6.4.7. Work Productivity and Activity Impairment Questionnaire

6.4.7.1. Definition

The generic version of the WPAI questionnaire ([Appendix I](#)) measures the overall effect of health on productivity at work and daily activities. The specific health problems version of the WPAI questionnaire allows investigators to attribute productivity and activity impairment issues to specific health conditions. After the employment status of a respondent is identified, 3 open-ended questions are asked concerning (1) hours absent from work due to health problems (or specific condition), (2) hours absent from work due to other reasons, and (3) hours actually worked. Two additional questions are included that ask about the impact of health on

Statistical Analysis Plan

productivity, 1 concerning productivity at work and the other concerning daily activities outside of work. The response format of each item of the WPAI questionnaire consists of an 11-point scale ranging from 0 (no impairment) to 10 (complete impairment) (Reilly et al 1993).

The following scores will be derived based on the WPAI:GH questionnaire. Multiply scores by 100 to express in percentages.

- percent work item missed due to health: $\frac{Q2}{Q2+Q4}$
- percent impairment while working due to health: $\frac{Q5}{10}$
- percent overall work impairment due to health: $\frac{Q2}{Q2+Q4} + \left[\left(1 - \frac{Q2}{Q2+Q4} \right) \times \frac{Q5}{10} \right]$
- percent activity impairment due to health: $\frac{Q6}{10}$

6.4.7.2. Analysis

For the patients who are currently employed, their scores of

- percent work item missed due to health
- percent impairment while working due to health
- percent overall work impairment due to health
- percent activity impairment due to health

will be analyzed using the same ANCOVA method as described in Section 6.2.2.

6.4.8. Patient’s Global Impression of Change

6.4.8.1. Definition

The PGIC scale (Appendix J) is a validated generic tool for assessment of overall change in the severity of illness following treatment. Patients will rate how they describe the change (if any) that their migraine/headaches have had in their general quality of life and health status since beginning the treatment in this study on a 7-point scale where 1=no change (or condition got worse); 2=almost the same, hardly any change at all; 3=a little better, but no noticeable change; 4=somewhat better, but the change has not made any real difference; 5=moderately better, and a slight but noticeable change; 6=better, and a definite improvement that has made a real and worthwhile difference; and 7=a great deal better, and a considerable improvement that has made all the difference.

Based on the PGIC assessment, a dichotomous scale of “ Yes” or “No” will be derived. A favorable change is score of 5-7 = ‘Yes’, which means there is significant improvement with the treatment. If the response is 1-4 = ‘No’, it is considered no significant change.

6.4.8.2. Analysis

The percentage of patients' dichotomous scale of “ Yes” or “No” rated by PGIC assessments will be analyzed using a logistic regression model as described in Section [6.3.1.2](#).

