9.5.4.4. Exploratory Efficacy Analysis

For the double-blind period, the continuous exploratory efficacy endpoints period will be analyzed similarly as the primary efficacy endpoint. For the proportions of responders for the double-blind period, a logistic regression model will be used similarly as the secondary efficacy endpoint.

For the open-label period, the exploratory efficacy endpoints will be summarized using descriptive statistics.

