2.4. Sample Size and Power Considerations

In the Phase 2b study for CM (study LBR-101-021), the treatment difference between 675/225/225 mg and placebo in change from baseline in monthly average migraine days was 2.1 days (standard deviation [SD]=5.2 days). In the phase 2b study for EM (study LBR-101-022), the treatment difference between 225 mg monthly dose and placebo in change from baseline in monthly average migraine days was 2.7 days (SD=4.1 days). In the Phase 3 study for CM (study TV48125-CNS-30049), the treatment differences to placebo in change from baseline in monthly average migraine days were 1.7 days and 1.8 days for the quarterly dose and the monthly dose, respectively (SD=5.4 days). In the Phase 3 study for EM (study TV48125-CNS-30050), the treatment differences to placebo in change from baseline in monthly average migraine days were 1.3 days and 1.5 days for the quarterly dose and the monthly dose, respectively (SD=3.4 days). Combining the information above, a treatment difference of 1.8 days is used. Considering the patient population is different from the previous studies, a SD of 6 days is used to account for the complexity and uncertainty of this study.

A sample size of 705 (235 patients per treatment group) evaluable patients completing the study is needed for 90% power to show a 1.8 difference in migraine days (assuming a common SD of 6 days) at an alpha level of 0.05. Assuming a 12% discontinuation rate, 268 patients per treatment group will be randomized in the study.

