6.2.2. Primary Efficacy Analysis

The hypothesis testing for the primary analysis is:

$$H_o : \delta_1 = \delta_2 \quad vs \quad H_a : \delta_1 \neq \delta_2$$

where δ_1 and δ_2 are the estimates of mean change from baseline in the monthly average number of migraine days for the fremanezumab treatment group and the placebo group respectively. The estimated difference of fremanezumab monthly dose versus the placebo and fremanezumab quarterly dose versus the placebo will be tested following the pre-specified fixed sequence as described in Section 7.

The primary efficacy endpoint will be analyzed using an analysis of covariance (ANCOVA) method. The model will include treatment, gender, region, special group of treatment failure (Yes or No), migraine classification (ie, CM or EM), and treatment-by-migraine classification interaction as fixed effects, and baseline number of migraine days and years since onset of migraines as covariates. The stratification factors (as randomized) will be used in the model. The treatment comparison between each fremanezumab treatment group (monthly dose and quarterly dose) and placebo for monthly average migraine days will be conducted under this model using the estimate statement. Ninety-five percent confidence intervals (CIs) will be constructed for the least square (LS) means differences between each fremanezumab treatment group (monthly dose and quarterly dose) and placebo.

Note: Special treatment failure group defined as patients who must have had inadequate response to valproic acid. In addition, patients in the special treatment failure group must have had inadequate response to 2 to 3 other classes of migraine preventive medications as defined in Appendix H of the protocol.

Type I error will be controlled for treatment comparisons by using Hochberg's method (see Section 7).

The following sample SAS code pertains to the primary analysis.

```
ODS OUTPUT DIFFS=XXX LSMEANS=XXX TESTS3=XXX;
```

```

PROC MIXED DATA=XXX;
    CLASS TREAT GENDER REGION TRTFAIL MIGCLASS;
    MODEL CHG=BASE YOD TREAT GENDER REGION TRTFAIL MIGCLASS
    TREAT*MIGCLASS/S;
    LSMEANS TREAT/PDIFF CL ALPHA=0.05;
RUN;

```

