- mean change from baseline (28-day run-in period) in the number of migraine days during the 12-week period after the 1st dose of study drug for the subset of patients who failed 2 to 3 classes of preventive medications and valproic acid for migraine in the past
- proportion of patients reaching at least 50% reduction in the monthly average number of migraine days during the 12-week period after the 1st dose of fremanezumab for the subset of patients who failed 2 to 3 classes of preventive medications and valproic acid for migraine in the past
- mean change from baseline (day 0) in disability score, as measured by the HIT-6, at 4 weeks after administration of the 3rd dose of study drug
- mean change from baseline (day 0) in disability score, as measured by the MIDAS questionnaire, at 4 weeks after the administration of the 3rd dose of study drug
- mean change from baseline (day 0) in quality of life, as measured by the MSQOL questionnaire, at 4 weeks after administration of the 3rd dose of study drug
- mean change from baseline (day 0) in the health status, as measured by the EQ-5D-5L questionnaire at 4 weeks after administration of the 3rd dose of study drug
- mean change from baseline (day 0) in patient depression status, as measured by the PHQ-2 and PHQ-9, at 4 weeks after administration of the 3rd dose of study drug
- mean change from baseline (day 0) in patient work productivity and activity impairment, as measured by the WPAI questionnaire, at 4 weeks after administration of the 3rd dose of study drug
- mean change from baseline (day 0) of patient satisfaction, as measured by the PGIC scale, at 4 weeks after the 3rd dose of study drug

The exploratory endpoints for the open-label period are as follows:

- mean change from baseline (28-day run-in period) in the monthly average number of migraine days during the 12-week period after the 4th dose of fremanezumab
- proportion of patients reaching at least 50% reduction from baseline (28-day run-in period) in the monthly average number of migraine days during the 12-week period after the 4th dose of fremanezumab
- mean change from baseline (28-day run-in period) in the monthly average number of headache days of at least moderate severity during the 12-week period after the 4th dose of fremanezumab
- mean change from baseline (28-day run-in period) in the monthly average number of days of use of any acute headache medications during the 12-week period after the 4th dose of fremanezumab

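### PGIC is listed as a change from a baseline that is never collected, and its only inferential analysis is a Yes/No cut; adding an ordinal model of the 7-point score is a cheap improvement

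*SAP*

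**What the plan says.** The endpoint lists in SAP 1.2 and 6.4, like protocol 2.2 and 9.5.3, give the PGIC endpoint as "mean change from baseline (day 0) of patient satisfaction, as measured by the PGIC" scale, 4 weeks after the third dose. Protocol 9.5.4.4 states that "the continuous exploratory efficacy endpoints period will be analyzed similarly as the primary efficacy endpoint", and it sends responder proportions to logistic regression.

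SAP 6.4.8.1 defines seven ordered categories rating change since the start of treatment. The upper ones include "5=moderately better, and a slight but noticeable change; 6=better, and a definite improvement". It then derives Yes for scores 5-7 and No for 1-4. Under SAP 6.4.8.2 the percentages "rated by PGIC assessments will be analyzed using a logistic regression model", namely that of Section 6.3.1.2. No visit is named there.

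Protocol Table 2 and Appendix B schedule PGIC at visits 3, 5 and 8, and not at visit 2. SAP 6.1 promises descriptive statistics for all efficacy data. SAP Section 17 lists two changes from the protocol, the database locks and the per-protocol set, and does not mention PGIC.

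**The concern.** There are two separate problems.

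- **The endpoint and its analysis do not match.** The SAP's endpoint lists name a mean change and its analysis section names a proportion. The clause in the SAP introduction that the SAP prevails over the protocol does not settle a disagreement inside the SAP. The listed quantity has no baseline to be a change from.
- **The only inference on PGIC drops most of the scale.** A score of 5 counts the same as 7, and 1 the same as 4. Movement within either half cannot show up in any test. HIT-6, MIDAS, MSQOL, the EQ visual analogue scale, PHQ-9 and WPAI are all tested as scores by ANCOVA (SAP 6.4.2 to 6.4.7). PGIC is the one questionnaire whose inference rests wholly on a dichotomy, and the SAP gives no reason.

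At stake is the precision of the trial's patient-rated global impression, using data that will be collected anyway.

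**Working it through.** **Inputs from the documents.** SAP 2.4: "Combining the information above, a treatment difference of 1.8 days is used", SD 6, 235 evaluable patients per arm, "at an alpha level of 0.05". The test is two-sided (SAP 6.2.2 states a not-equal alternative).

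**The plan's own figure.** n = 2 × (1.960 + 1.282)² × 6² / 1.8² = 233.5, so 234 per arm by the normal approximation. The t-test needs 235 (power 90.07%). Then 235 / 0.88 = 267.05, so 268 randomised. The plan's sample size reproduces, but it concerns migraine days.

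**Inputs that are assumptions.** The documents give no PGIC effect, SD, placebo Yes share or power. I assume:
- a latent-normal shift d = 1.8/6 = 0.30 SD, borrowed from migraine days;
- a placebo Yes share of 20-60%;
- two spreads within the halves: flat, or bottom-heavy (40/30/20/10% across scores 1-4 and 50/30/20% across 5-7).

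**Power of the cut.** Active Yes share p₁ = Φ(Φ⁻¹(p₀) + d). Power = Φ{[p₁ − p₀ − 1.96 √(2p̄(1−p̄)/n)] / √([p₀(1−p₀) + p₁(1−p₁)]/n)}, where p̄ is the mean of the two shares.

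Example with p₀ = 0.40: p₁ = Φ(−0.253 + 0.30) = 0.519 and p̄ = 0.459. Power = Φ[(0.1186 − 1.96 × 0.0460) / 0.0456] = Φ(0.62) = 73%.

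**Power on the full scale.** I use the Wilcoxon test, which is close to the proportional-odds score test. Let θ = P(active > placebo) + ½P(tie). Power = Φ[(θ − 0.5 − 1.96 SE₀) / SE₁], with SE₀ and SE₁ the standard errors under the null and the alternative, corrected for ties.

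Same example, flat spread (15% in each of 1-4, 13.3% in each of 5-7): θ = 0.5816, SE₀ = 0.02635, SE₁ = 0.02605. Power = Φ(0.0300 / 0.02605) = Φ(1.15) = 87.5%.

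**Results at d = 0.30, n = 235 per arm**

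| Placebo Yes | Active Yes | Cut | Full scale | Loss (points) |
|---|---|---|---|---|
| 20% | 29.4% | 65.8% | 86.7-87.5% | 21-22 |
| 30% | 41.1% | 71.3% | 87.0-87.6% | 16 |
| 40% | 51.9% | 73.4% | 87.2-87.5% | 14 |
| 50% | 61.8% | 73.2% | 87.3% | 14 |
| 60% | 71.0% | 70.9% | 86.9-87.2% | 16 |

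Simulation under the same assumptions agrees to within about a point: 65-74% for the cut, 87-88% for the full scale, loss about 15-22 points.

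**Sensitivity**
- Logistic latent scale at 0.30 SD: loss about 8-20 points by formula, 8-22 by simulation.
- Larger normal shift: about 10-16 points at 0.35, 5-9 at 0.40, 2-4 at 0.45 and under 2 at 0.50, as both analyses approach 100%.
- Placebo Yes share outside the assumed range: power of the cut at 0.30 falls to 53% at a 10% share and 57% at an 80% share.
- An effect confined to the 4/5 boundary: the loss shrinks and the cut may be the better analysis.

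**The case against.** **The cut follows the scale's own anchors.** Category 3 describes no noticeable change. Category 4 says the improvement made no real difference. Category 5 is the first in which the change is called noticeable. The split is prespecified and gives a percentage clinicians can read. This stands, and it is why the responder analysis should stay.

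**The SAP did not throw away a workable analysis.** A reader might infer that the protocol prescribed a mean on the 7-point scale and the SAP replaced it. The documents do not support that. The protocol's quantity is a change from day 0 that cannot be formed, and the primary-type ANCOVA adjusts for a baseline that PGIC lacks. The SAP gave an analysis to an endpoint that had none. What remains is that the unusable wording was kept and the choice was not declared.

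**The 0.30 SD is not the trial's PGIC effect.** A reader might take the power loss as one at the planned effect size. No such size exists for PGIC. The SD of 6 was set above every earlier SD quoted in SAP 2.4. The earlier results there give larger standardised effects on migraine days: 1.7/5.4 = 0.31, 1.8/5.4 = 0.33, 1.3/3.4 = 0.38, 2.1/5.2 = 0.40, 1.5/3.4 = 0.44 and 2.7/4.1 = 0.66. None of these need carry over to PGIC, and nor need 0.30. At the upper end the loss is negligible.

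**A pure latent shift suits an ordinal test.** True. The calculation also leaves out covariates and missing data, so the ranges are illustrations and not bounds.

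**Conclusion.** This is a cheap improvement and not a flaw in the trial's main inference. Two things follow from the documents alone. The listed PGIC endpoint cannot be computed. The only inferential PGIC analysis is an undeclared Yes/No split with no visit attached.

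The size of the power loss rests on assumptions: about 14-22 points at a 0.30 SD normal latent shift with 235 per arm and 20-60% Yes on placebo, about 8-22 with a logistic latent scale, and under 2 by 0.50 SD.

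Two further inferences would go too far. The first is that the full scale is never used: SAP 6.1 promises descriptive statistics for all efficacy data, so what is missing is full-scale inference. The second is that the trial's conclusions are weakened: PGIC is exploratory and lies outside the multiplicity procedure (SAP Section 7), so no primary or secondary claim is affected.

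**What to change.** - **SAP 6.4.8.2:** keep the 5-7 responder logistic regression. Add a proportional-odds model of the 7-point score at visit 5 (4 weeks after the third dose), with the Section 6.3.1.2 terms: treatment, gender, region, special treatment failure group and CM/EM, as randomised. Report the common odds ratio and 95% CI for each dose against placebo, and name visit 5 for the responder model too.
- **SAP 1.2 and 6.4:** reword the endpoint as the PGIC score at 4 weeks after the third dose, without a change from day 0. The parallel open-label entry (sixth dose) has the same wording and needs the same correction.
- **SAP Section 17:** list the change.

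The cost is a few lines of SAP text and one more model on data already scheduled for collection. SAP 2.5.2 requires SAP amendments to be approved before the first interim lock, so this should be settled by then. The downside is that a common odds ratio assumes proportional odds and is less familiar than a responder percentage, which is why both are reported.

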7. MULTIPLE COMPARISONS AND MULTIPLICITY

The Hochberg's method along with hierarchical testing procedure for multiple comparisons between treatment groups (2 comparisons: fremanezumab monthly dose compared with placebo and fremanezumab quarterly dose compared with placebo) for the primary and secondary endpoint analyses will be used to maintain the experiment-wise type I error of 5%. In the primary analysis, according to the Hochberg's method, if the null hypothesis is rejected for both the fremanezumab monthly and quarterly treatment groups at an alpha level of 5%, then no adjustment to the alpha level will be performed and both comparisons will be declared as statistically significant. The secondary variables will then be tested in the order as specified in Section 6.3 for both the fremanezumab monthly and quarterly treatment groups using the same procedure as the primary analysis. If the null hypothesis is not rejected for 1 of the doses at an alpha level of 5%, then the other dose will be tested using an alpha level of $5\%/2=2.5\%$, and the sequential testing will stop.

No multiplicity adjustments will be made for exploratory efficacy analyses.

8. SAFETY ANALYSIS

8.1. General

The safety analysis sets will be used for all safety analyses. Summaries will be presented separately for the double-blind treatment period and open-label treatment period. For the double-blind treatment period, summaries will be presented by migraine classification (ie, CM, EM, and all), treatment group and all fremanezumab, unless otherwise stated. For the open-label treatment period, summaries will be presented by migraine classification (ie, CM, EM, and all), double-blind treatment group (ie, placebo, fremanezumab 675 mg/placebo/placebo, fremanezumab 675/225/225 mg, fremanezumab 225/225/225 mg, all fremanezumab), and overall (ie, total).

8.2. Duration of Exposure to Study Drug

Duration of treatment (days treated) for the double-blind treatment period is the number of days on treatment started from the 1st study drug administration day to month 3 (visit 5) visit day (month 3 visit day – first day of study drug + 1). Duration of treatment (days treated) for the open-label treatment period is the number of days on treatment started from the 1st study drug administration day in the open-label treatment period to the EOT visit day/early withdrawal day (EOT visit day – first day of study drug in the open-label treatment period + 1). For patients who are lost to follow-up, the EOT visit date is defined as the last study drug administration + 27.

Number (%) of patients receiving 1 dose, 2 doses, and 3 doses during the double-blind and open-label treatment periods will be summarized using descriptive statistics. Duration of treatment (days) will also be summarized using descriptive statistics.

8.3. Adverse Events

All adverse events will be coded using the MedDRA.

The following are considered protocol-defined adverse events of special interest: ophthalmic adverse events of at least moderate severity, events of possible drug-induced liver injury (aspartate aminotransferase [AST] or alanine aminotransferase [ALT] ≥ 3 x the upper limit of the normal range [ULN], total bilirubin ≥ 2 x the ULN or international normalized ratio [INR] > 1.5), Hy's Law events, or events of suspected anaphylaxis and severe hypersensitivity reactions.

Summaries will be presented for all treatment-emergent adverse events (overall and by severity), adverse events determined by the investigator to be treatment-related adverse events (defined as related or with missing relationship (overall and by severity), serious adverse events, protocol-defined adverse events of special interest, adverse events causing withdrawal from treatment, and non-serious adverse events. Additionally the injection site reactions recorded as adverse events will be summarized separately.

The incidence of adverse events will be summarized using descriptive statistics by system organ class, preferred term, and severity of the adverse event. Each patient will be counted only once within a system organ class or a preferred term using the adverse events with the highest severity within each category. Adverse events with the missing flag indicating serious will be excluded

from the summary of serious adverse events but included in the summary of non-serious adverse events.

Listings for deaths, adverse events, serious adverse events, adverse events causing withdrawal from treatment, injection site-related adverse events, and protocol defined adverse events of special interest will be presented. In addition, MedDRA dictionary terms for adverse event descriptions and adverse events preferred terms by patient number and treatment group will be presented.

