The onset and end dates, duration (in case of adverse event duration of less than 24 hours), action taken regarding IMP, treatment administered, and outcome for each adverse event must be recorded both on the source documentation and the CRF.

The relationship of each adverse event to IMP and study procedures, and the severity and seriousness of each adverse event, as judged by the investigator, must be recorded as described below.

Further details are given in the Safety Monitoring Plan.

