7.1.5.1. Definition of a Serious Adverse Event

A serious adverse event is an adverse event occurring at any dose that results in any of the following outcomes or actions:

- results in death
- is life-threatening adverse event (ie, the patient was at risk of death at the time of the event); it does not refer to an event which hypothetically might have caused death if it were more severe

- requires inpatient hospitalization or prolongation of existing hospitalization, which means that hospital inpatient admission or prolongation of hospital stay were required for treatment of an adverse event, or that they occurred as a consequence of the event
- Hospitalizations scheduled before the patient signed the informed consent form will not be considered serious adverse events, unless there was worsening of the preexisting condition during the patient’s participation in this study.
- results in persistent or significant disability/incapacity (refers to a substantial disruption of one’s ability to conduct normal life functions)
 - is a congenital anomaly/birth defect
 - an important medical event that may not result in death, be life-threatening, or require hospitalization, but may jeopardize the patient and may require medical intervention to prevent one of the outcomes listed in this definition

Examples of such events are intensive treatment in an emergency room or at home for allergic bronchospasm; blood dyscrasias or convulsions that do not result in hospitalization; or the development of drug dependency or drug abuse. Note: Any suspected transmission of an infectious agent via a medicinal product is considered an important medical event.

All occurrences of possible drug-induced liver injury that meet Hy’s law criteria, defined as **all** of the below, must be reported by the investigator to the sponsor as a serious adverse event:

- alanine aminotransferase (ALT) or aspartate aminotransferase (AST) increase of >3x the upper limit of normal (ULN)
- total bilirubin increase of >2x ULN
- absence of initial findings of cholestasis (ie, no substantial increase of alkaline phosphatase [ALP])
- no other explanation for the observed abnormalities

An adverse event that does not meet any of the criteria for seriousness listed above will be regarded as a nonserious adverse event.

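### Adverse events with a missing seriousness flag are tabulated as non-serious, although the same SAP section counts a missing relationship as related

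*SAP*

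**What the plan says.** The rule is one sentence in SAP Section 8.3 that runs over a page break. The first part reads "Adverse events with the missing flag indicating serious will be excluded" and the rest "from the summary of serious adverse events but included in the summary of non-serious adverse events". Read together, the event is not merely left out of the SAE table. It is placed in the non-serious table.

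Earlier in the same section, treatment-related events are "defined as related or with missing relationship". Protocol Section 9.7 has the same rule for relationship and no rule for missing seriousness.

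Two other protocol statements matter. Section 7.1.2 makes the field mandatory: "the severity and seriousness of each adverse event, as judged by the investigator, must be recorded as described below". Section 7.1.5.1 says when an event is nonserious: "An adverse event that does not meet any of the criteria for seriousness listed above will be regarded as a nonserious adverse event".

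SAP Section 17, which lists changes from the protocol's analyses, neither mentions nor explains the missing-seriousness rule.

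**The concern.** Two fields on the same adverse event record can be blank, and SAP 8.3 resolves them in opposite directions. A blank relationship goes to the less favourable category and a blank seriousness flag to the more favourable one. A safety table normally either takes the cautious default for an unknown or shows the unknown openly. This rule does neither, because once the event is in the non-serious table a reader of that table cannot tell that its seriousness was never established.

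The SAE summary is among the first safety outputs that a regulator reads. A truly serious event with a blank flag would be missing from it and would appear as non-serious. The section contains no step that checks a blank flag against the separate SAE report form. As written, an event with a submitted SAE report but a blank flag would be tabulated as non-serious.

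**Working it through.** The plan states no figure to reproduce. The check is a comparison of texts, followed by simple arithmetic for scale.

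**1. The two missing-data rules in SAP 8.3**

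| Field left blank | Counted as | Direction |
|---|---|---|
| Relationship to study drug | Related | Less favourable |
| Seriousness | Non-serious | More favourable |

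**2. Whether the protocol supplies the default.** Protocol 7.1.5.1 classes an event as nonserious when it meets none of the listed criteria. That is the result of an assessment. A blank flag means that no result was recorded. The definition does not cover this case, so it neither prescribes nor forbids the SAP rule. Protocol 9.7 is silent on it.

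**3. Scale.** The one input is the planned arm size in SAP 2.4: "268 patients per treatment group will be randomized in the study". The number of affected patients, k, is an assumption, because the documents give no rate of missing flags. An affected patient is one whose only serious event in the summary period has a blank flag. Compared with counting that event as serious, the arm's overall SAE incidence is lower by k/268:

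- k = 0: 0
- k = 1: 1/268 = 0.37 percentage points
- k = 3: 3/268 = 1.12 percentage points
- k = 5: 5/268 = 1.87 percentage points

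**4. Limits on these figures.**

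- Incidence counts patients. A patient who already has a flagged SAE in the same table does not change the overall rate, so 0.37 points is the most that one patient can contribute in an arm of 268.
- 268 is the number planned for randomization. Under SAP 3.3 the denominator is patients treated, grouped by treatment received, so the actual divisor may differ slightly.
- SAP 8.1 also splits the safety tables by migraine class. With the planned split of about 50:50, a class within an arm has about 268/2 = 134 patients, and one patient is worth at most 1/134 = 0.75 percentage points there.

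**The case against.** The best defence is that the two fields differ in kind. Relationship is the investigator's causal judgement, and if it is blank nothing else on record can supply it. Seriousness rests largely on observable outcomes such as death or hospitalization, and it has a second capture route: a separate form sent to the sponsor within 24 hours (Protocol 7.1.5.3.1). A blank flag with no SAE form therefore more likely belongs to a non-serious event. In addition, Protocol Appendix P sends missing data back to the center as queries and requires the investigator to approve the data as complete. The events also stay visible: they remain in the all-event summary and the listings, and deaths, withdrawals and events of special interest have outputs of their own.

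Much of this stands. Missing flags should be rare, and a truly serious event would be misplaced only after several controls had failed. But the rule applies precisely to what is left after those controls, so they cannot justify its direction. The argument from the SAE form is a good reason to check the form, and SAP 8.3 does not ask for that.

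A reader might infer three stronger things, none of which the documents support:

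- **That SAE incidence will be biased downward.** This holds only if some blank-flag events are truly serious. If they are all non-serious, the rule classifies them correctly.
- **That the rule favours fremanezumab over placebo.** Patients, investigators and study staff are blinded in the double-blind period (SAP 2.2), so there is no stated reason for blanks to fall more often in one arm.
- **That the SAP contradicts the protocol.** The protocol has no rule for missing seriousness. The inconsistency is within SAP 8.3.

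**Conclusion.** The point holds as a minor one. SAP 8.3 sends events of unknown seriousness to the favourable category, does the reverse for unknown relationship, and gives no reason. If a blank-flag event is truly serious, SAE incidence is understated by at most 0.37 percentage points per affected patient in an arm of 268. There is no understatement if every flag is resolved before lock, or in the overall rate if the patient has another SAE in the same table. How many patients would be affected cannot be estimated from the documents. Efficacy results are untouched.

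It would also be wrong to conclude that every blank should simply be counted as serious. Without a check against the SAE forms, that could put events in the SAE table that no investigator judged serious and that do not match the safety reports.

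**What to change.** Replace the sentence in SAP 8.3 with a rule in two steps:

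1. Before each database lock, query every missing seriousness flag and reconcile it against the SAE report forms.
2. Count any flag still missing as serious in the SAE summary, or show these events in a separate row for seriousness missing. Mark them in the listing and leave them out of the non-serious summary.

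The cost is a short edit to one SAP paragraph and a reconciliation check before each lock, with no new data collection. If remaining blanks are counted as serious, the SAE table may be slightly overcounted. The reconciliation step limits this, and the separate row avoids assigning these events to either category.
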